A limiting factor in the use of epidural analgesia, however, is the high incidence of associated hypotension. Hypotension is defined as systolic blood pressure (SBP) > 20% below the baseline preoperative measurements and acquired before the epidural or any sedation has been administered. Effective segmental epidural block would thus invariably cause sympathectomy due to its location in the thoracic or lumbar areas by blocking the cardiac sympathetic nerves, the pre-ganglionic nerves to the adrenal glands or the sympathetic nerves to the blood vessels individually or in combination.

It has been proven beyond doubt that epinephrine, when added to ropivacaine 0.2% and used for epidural analgesia by infusion, is safe and may even improve spinal cord blood flow and the analgesic effects of ropivacaine.⁷ It is also known that the cause of hypotension associated with epidural analgesia is the blockade of the sympathetic outflow to the cardiovascular and adrenal systems, and that the ideal mechanism to counter this would be by beta1-stimulation, which is ideally achieved with low-dose epinephrine.

Finally, it is known that epidural infused epinephrine increases its serum concentration.⁸ What is not known is whether added epinephrine will counteract this sympathetic blockade and prevent hypotension, and what the optimal concentration of epinephrine infusion would be during epidural analgesia with 0.2% ropivacaine to achieve optimal analgesia and optimal hemodynamic status.

5. Specific Aims:

We aim to examine whether adding epinephrine will counteract the sympathetic blockade and prevent hypotension, and what the optimal concentration of epinephrine infusion would be during epidural analgesia with 0.2% ropivacaine that can achieve both optimal analgesia and optimal hemodynamics. Specifically we plan to answer the following questions:

- 1. Does the addition of epinephrine to the epidural infusion of 0.2% ropivacaine:
 - a. Prevent hypotension?
 - b. Lead to a wider spread of local anesthetic effect?
 - c. Lead to a difference in the average pain scores?
 - d. Lead to a difference in when ambulation occurs?
 - e. Decrease potential of other opioid-related side effects such as pruritus, nausea/vomiting, respiratory depression and opioid consumption?
- 2. What is the optimal concentration of epinephrine (2mcg/mL or 5mcg/mL) to achieving the above-mentioned outcomes?

6. Research Plan:

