Patients will receive a bolus of 500 mL of 5% Albumin intravenous infusion as per the usual routine practice of the APS before the main bolus dose is injected. A preoperative level of block will be established that is appropriate for the surgery by injecting an appropriate volume of ropivacaine 0.5% or lidocaine 2% w/ epinephrine 1:200,000 (5–10 mL) into the epidural space as per the usual practice of the APS. This will be done after the routine test dosing with 3 mL of 2% lidocaine and 1:200,000 epinephrine, confirmed that intrathecal and intravascular markers are negative. If an insensate-to-cold area in the appropriate dermatomes cannot be established within 10 minutes following a 5 to 10 mL (maximum 10 mL) injection of ropivacaine 0.5%, the epidural catheter will be removed and replaced. If this process is repeated and there was still no level, it will be annotated and the patient will be removed from the study, labeled as a primary block failure, and treated appropriately by the attending anesthesiologist by either repeating the epidural block placement a third time or using other appropriate perioperative analgesia.

Research-Related Procedures - Preoperative Period:

Once consent is obtained, patients will be randomly allocated by computergenerated randomization to one of four groups. This will be a quintuple blinded prospective study. The anesthesiologist managing the intraoperative anesthesia, the anesthesiologists (APS) placing the blocks and following the patients on the floors, the research nurse taking the measurement, the surgeons, nor the patients will be aware of what combination of drugs are used for the epidural block infusion.

The three groups will consist of:

- 1. Group A (Ropivacaine 0.2% infusion; Control group)
- 2. Group B (Ropivacaine 0.2% + 2 mcg/mL epinephrine)

3. Group C (Ropivacaine 0.2% + 5 mcg/mL epinephrine)

The pharmacists will make up and supply test drugs for groups A, B and C and provide them labeled to the block area drug dispenser as "A, B, or C test solutions" without specifically identifying the content.

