All data will be entered securely using the online database or Red Cap. To assess potential dose-response effects on changes in continuously measured primary outcomes, repeated measures mixed modeling analyses will be used. This type of analysis can assess the main effects of time (i.e., change) and group (i.e., epinephrine dose; coded as an ordinal variable) on the outcomes. Mixed models are the preferred approach to analyze data with repeated measures; these models can account for correlation among repeated measurements, flexible time effects, and can handle missing data. Additionally, this model can estimate time × group interactions. If this interaction is statistically significant, that provides evidence that the changes in outcomes are different depending on the dose of epinephrine that a patient received. Logistic regression models will be used to assess the relationship between epinephrine dose and incidence of hypotension (SBP < 20% or MAP < 55 mmHg) and other categorical outcome variables. A P value of <0.05 was considered statistically significant for all statistical tests. All analyses were conducted in JMP Pro 11.0 (SAS Institute, Cary, NC).

Sample size determination

At 80% power (alpha = 0.05), a sample of n=200 (50 per group) will be able to detect 26% differences in incidence of categorical outcomes, and an effect size of Cohen's f = 0.24 for group mean differences and effect size of Cohen's f = 0.09 for group differences mean change over time. Figure 1 depicts how these effect sizes will translate to the outcomes, with assumed standard deviations in outcomes ranging from 5 to 25. For example, assuming MAP has an SD = 10, the present study will be able to detect mean differences of 5 mmHg across groups and group differences of 3 mmHg for mean change over time.

ADMINISTRATIVE RESPONSIBILITIES:

Study Resources: The principal investigator will oversee the data collection, data analysis and will maintain the records in confidence. Should any evidence suggest that the study protocol require modification, the PI will notify the IRB in a timely manner for review and approval. Each subject will be identified by number, not by name, on all data forms. To protect confidentiality, all data will be numerically coded and information linking the numeric codes to individual participant's names will be kept in a locked file in the PI's office.

7. Possible Discomforts and Risks:

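### Ordinal dose coding is left undefined and no contrast answers Aim 1 or Aim 2; fitted as a single score, it could miss a benefit that peaks at 2 mcg/mL

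*Combined protocol and SAP*

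**What the plan says.** Aim 1 (Section 5) is a question about epinephrine against none: "Does the addition of epinephrine to the epidural infusion of 0.2% ropivacaine" prevent hypotension, among other effects. Aim 2 asks which of 2 and 5 mcg/mL is better, so it allows for 2 being better than 5.

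The Data analysis plan in Section 6 states: "To assess potential dose-response effects on changes in continuously measured primary outcomes, repeated measures mixed modeling analyses will be used". Dose enters that model as "group (i.e., epinephrine dose; coded as an ordinal variable", and a time-by-group interaction can be estimated. No scores, degrees of freedom or contrasts are given. Incidence of hypotension goes to a separate logistic regression on dose, again without stated coding.

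The sample size paragraph reads "At 80% power (alpha = 0.05), a sample of n=200 (50 per group" and reports a detectable Cohen's f of 0.24 for group means and a 26% difference in incidence. On the number of arms, the preoperative research procedures say patients are "randomly allocated by computergenerated randomization to one of four groups", but then "The three groups will consist of" introduces a list of A (no epinephrine), B (2 mcg/mL) and C (5 mcg/mL).

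**The concern.** An ordinal predictor can be fitted in two ways. As one numeric score it uses 1 df and tests for a straight-line trend. As an ordered factor it uses one parameter per step, and its overall test is the same as for unordered groups. The stated purpose, dose-response, leans towards the first; the power figure leans towards the second.

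Under a single score the test can be weak, or nearly blind, when the middle dose does best. Aim 2 leaves that pattern open. A non-significant trend could then be read as a negative answer to Aim 1 although one concentration works. Under either coding, the plan names no comparison that answers Aim 2 or sets each concentration against control.

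**Working it through.** **Inputs.** From Sample size determination: alpha 0.05, power 80%, N = 200 at 50 per group, f = 0.24, MAP SD 10 mmHg, difference 5 mmHg, incidence difference 26 points. From the group list: 0, 2 and 5 mcg/mL. Assumed: two-sided or omnibus tests (sidedness is not stated), equal arms, one summary value per patient. Because the arm count is inconsistent, I use 50 per arm as stated and also 67 (200/3 = 66.7).

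**1. The plan's own figure.** Noncentral F with λ = N·f². For four groups, N = 200 and 3 df, 80% power needs f = 0.236, which rounds to 0.24. At f = 0.24, λ = 200 × 0.0576 = 11.52 and power is 81.5%. The alternatives fit less well: 1-df trend, 0.199 (N = 200) or 0.230 (N = 150); three-group 2-df test, 0.221 (N = 200) or 0.256 (N = 150). The stated f is therefore that of an omnibus four-group test.

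**2. What a single score tests.** With centred scores c, λ(trend) = n(Σcμ)²/(σ²Σc²); for the 2-df test, λ = nΣ(μ − mean)²/σ².
- Scores 0, 1, 2: c = −1, 0, 1, so Σcμ = C − A. Group B drops out.
- Scores 0, 2, 5: c = −7/3, −1/3, 8/3 and Σc² = 114/9 = 12.67. Group B has almost no weight.

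**3. Continuous outcome.** B − A = 5/10 = 0.5 SD. Example at 50 per arm with C keeping half the effect:
- 2-df: λ = 50 × (0.25² + 0.25²) = 6.25, power 59.3%.
- Scores 0, 1, 2: λ = 50 × 0.25²/2 = 1.56, power 23.7%.
- Scores 0, 2, 5: Σcμ = −0.5/3 + 8 × 0.25/3 = 0.5, λ = 50 × 0.25/12.67 = 0.99, power 16.7%.

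Power by scenario (trend shown as scores 0,1,2 / scores 0,2,5):

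| Effect at 5 mcg/mL | 2-df, n = 50 | Trend, n = 50 | 2-df, n = 67 | Trend, n = 67 |
|---|---|---|---|---|
| None | 72.7% | 5.0 / 6.2% | 85.3% | 5.0 / 6.7% |
| Half of B's | 59.3% | 23.7 / 16.7% | 73.2% | 30.2 / 20.8% |
| Three quarters of B's | 63.0% | 46.1 / 37.6% | 76.8% | 57.9 / 47.9% |
| Same as B's (plateau) | 72.7% | 70.0 / 63.4% | 85.3% | 82.1 / 76.1% |
| Linear: B 0.25 SD, C 0.5 SD | 59.3% | 70.0 / 69.4% | 73.2% | 82.1 / 81.6% |

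**4. Hypotension incidence, if the logistic model also used a single score.** The documents give no control rate; 50% is my assumption, and 24% is 50% less the plan's 26 points. Power is from 100,000 simulated trials per scenario, 50 per arm, using the Cochran–Armitage and 2-df chi-square tests. Logistic likelihood-ratio tests, run for the first three patterns, agree within 2 points.
- 50/24/50%: trend 6–7%, 2-df 81%.
- 50/24/37%: trend 20–28%, 2-df 69%.
- 50/24/24%: trend 74–79%, 2-df 82%.
- 50/37/24% (linear): trend 78%, 2-df 69%.

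Varying the control rate from 30% to 80% with the same 26-point fall at B: if C equals control, trend is 3–10% and 2-df 78–98%; if C keeps half the benefit, trend is 18–43% and 2-df 64–93%. The gap does not depend on the 50% assumption.

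**The case against.** The strongest reply is that nothing in the documents says the test is a 1-df trend. Ordinal coding can mean an ordered factor with k − 1 parameters, whose global test is sound. The stated f of 0.24 matches an omnibus test, and the interaction is described as showing that changes differ by dose, not as a slope. This stands, and it makes the loss of power conditional.

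Four further points also stand:
- The ordinal coding is attached only to the continuous outcomes. The most direct test of Aim 1a, hypotension incidence, is in the logistic model, whose coding is unknown.
- Near-zero power requires 5 mcg/mL to be close to control, not merely second best.
- For a plateau with equal-step scores the loss is about 3 points; only the 0, 2, 5 scores bring it to 8–9.
- The Background does say that "the ideal mechanism to counter this would be by beta1-stimulation, which is ideally achieved with low-dose epinephrine", but this does not separate 2 from 5 mcg/mL or predict a loss of effect at 5. The Abstract lists 5 mcg/mL as a current routine option.

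A trend test is also a defensible choice in a dose-finding study, and it is the more powerful one if the response is linear.

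These points do not remove the gap. A reader cannot tell whether the main test has 1 or 2 df, and no stated contrast answers either aim.

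**Conclusion.** The point holds as a gap in specification with a conditional consequence. The dose coding is undefined in one model and absent in the other, and the comparisons that Aims 1 and 2 ask for are not prespecified. If a single score is fitted and the benefit peaks at 2 mcg/mL, the power lost at 50 per arm for a 5 mmHg effect is about 66–68 points when 5 mcg/mL is inert, 36–43 when it keeps half the effect, and 17–25 when it keeps three quarters.

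A reader might infer more: that ordinal coding by itself makes the test a monotone trend, so that the trial would report no effect of epinephrine whenever 2 mcg/mL is best. The documents do not support that. They do not fix the degrees of freedom, their power figure points to an omnibus test, the coding is not stated for hypotension incidence, and a second-best effect at 5 mcg/mL reduces trend power without removing it.

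The sizes rest on equal arms, SD 10, a 5 mmHg effect and one summary value per patient. The incidence figures also rest on the assumed control rate.

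**What to change.** State in the Data analysis plan, before unblinding, that group is a three-level factor in both the mixed model (main effect and time-by-group) and the logistic model. Then:
- Test each outcome globally on the group factor (2 df for the group effect). This is the kind of test on which the stated f is based.
- Prespecify B v A and C v A for Aim 1 and B v C for Aim 2, with multiplicity control. With three arms, testing these pairs at 0.05 only after the 2-df test is significant is a closed procedure, which controls the error rate within an outcome.
- Report the linear trend, with its scores named, as supportive.
- Reconcile the number of arms and restate the detectable effect: with three arms it is f = 0.221 at N = 200 or 0.256 at N = 150.

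This changes wording only and needs no added patients. If the response is truly linear, the global test loses about 11 points for MAP (70.0% to 59.3%) and 9 for incidence (78% to 69%). If ordinal already means k − 1 parameters, the global test loses nothing. The pairwise contrasts are not strongly powered: B v A for 5 mmHg has 70% power at 50 per arm and 82% at 67, before requiring the global test first.

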Immediately following the establishment of an appropriate level for the planned surgery, an infusion of the test drug will be initiated at 4 to 8 mL per hour with a 4- to 8-mL patient-initiated bolus at a lockout interval of 1 hour – typically 8 mL per hour for major abdominal or thoracic surgery and thoracic epidural placement and 4 mL per hour for hip arthroplasty and lumbar epidural. Once established as effective for the clinical situation, this infusion will be left unchanged throughout the surgery and postoperative period. If clinically indicated, and the infusion rate is changed to below the limits of 4 – 8 mL per hour, this indicates the end of the need for the epidural infusion or otherwise untreatable hypotension.

Standard of Care - Intraoperative and Postoperative Periods:

Intraoperative and postoperative fluid management will be at the discretion of the anesthesia and primary teams.

Preoperative sedation will be a maximum of 5 mg of midazolam by intravenous injection (IV) and alfentanil 2000 mcg IV. Monitors include: EKG, non-invasive blood pressure, ETCO2, pulse oximeter, arterial line with Flow-Track (if indicated and appropriate per intra- or postoperative operative anesthesiologist), peripheral intravenous or central venous line as deemed appropriate by the attending intra- or postoperative operative anesthesia and mode of anesthesia (maintenance, fluid management, intraoperative analgesia, muscle relaxation, etc., are at the discretion of the attending intraoperative anesthesiologists.

If hypotension (see definition below) is encountered intraoperatively, the attending anesthesiologist will start a vasoactive or positive inotropic medication as indicated by the patient's medical requirements.

Research-Related Procedures – Intraoperative:

- Anesthesiologists will be encouraged to use alpha agonists if the other causes of hypotension are excluded and lumbar epidural is judged to be a contributory cause of the hypotension; and epinephrine, dobutamine, or dopamine (or indirect inotropic agents such as ephedrine) if thoracic epidural is judged to be the cause of the hypotension and the other causes of hypotension such as hypovolemia have been ruled out.

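### Dose effects on change are read from the time × group interaction, which tests a sustained infusion effect inefficiently; a baseline-adjusted comparison of post-infusion means would do better

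*Combined protocol and SAP*

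**What the plan says.** The Data analysis plan (section 6) fits a repeated measures mixed model with time, group and their interaction. Group is epinephrine dose, described as ordinal, and time effects are described as flexible. The only rule given for a dose effect on change is this: "If this interaction is statistically significant, that provides evidence that the changes in outcomes are different depending on the dose of epinephrine". The group main effect is also listed. No contrast, analysis window or baseline adjustment is named, and neither the number of periods nor the coding of time is given. The significance rule is general: "A P value of <0.05 was considered statistically significant for all statistical tests".

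The treatment is a continuous infusion started before surgery. Once it is effective, "this infusion will be left unchanged throughout the surgery and postoperative period" (Research-Related Procedures - Preoperative Period).

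Sample size determination gives detectable effects at 80% power: "a sample of n=200 (50 per group) will be able to detect 26% differences in incidence of categorical outcomes", "an effect size of Cohen's f = 0.24 for group mean differences" and "effect size of Cohen's f = 0.09 for group differences mean change over time". Incidence of hypotension is analysed separately, by logistic regression on dose.

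**The concern.** A treatment that starts once and then runs at a fixed rate most naturally produces a shift that begins at infusion start and persists. An interaction with categorical time asks a wider question, namely whether the arms differ in any pattern over time. Most of its degrees of freedom go to patterns other than a step, so part of the information about a step is spent on them.

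The group main effect does not fully repair this. Fitted to all periods, it averages in pre-infusion values that cannot carry a treatment effect. At stake is a real, steady effect on blood pressure or heart rate that the collected data could show but the stated test misses more often than it needs to.

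**Working it through.** **1. The plan's own figures.**

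- Group means, one-way ANOVA, λ = f²N: 0.24² × 200 = 11.52 on 3 and 196 df gives 81.5% power. This reproduces the stated 80% with four groups of 50.
- Change over time, λ = f²Nm/(1−ρ): with six periods and ρ = 0.5 (both assumed), 0.09² × 200 × 6/0.5 = 19.44 on (4−1)(6−1) = 15 df gives 81.0%. With three arms of 50, eight periods and ρ = 0.5, λ is again 19.44, and 14 df gives 82.3%.

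So f = 0.09 is consistent with an interaction test on many df. If all of that λ lay in one 2-df comparison, power would be 98%.

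**2. Inputs for the comparison.**

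- From the documents: alpha 0.05, 50 per arm, and the three arms listed.
- Degrees of freedom: the primary-measurement rows of the activity table mark six periods, giving (3−1)(6−1) = 10 df. Adding postoperative days 1 to 3 makes nine periods and 16 df.
- Assumed: eight periods (14 df), two of them before the infusion; exchangeable correlation ρ; SD 1; steady effects of 0, 0.2 and 0.4 SD.
- Arm effects deviate from their mean by −0.2, 0 and 0.2, so the sum of squares is 0.08 and 50 × 0.08 = 4. Each λ below is 4 divided by the relevant variance. Power uses the noncentral chi-square.

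**3. Results at ρ = 0.5.**

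- Interaction: the step has sum of squares over time 2 × 6/8 = 1.5. λ = 4 × 1.5/(1−0.5) = 12 on 14 df: **57%**.
- Group main effect, all periods: the effect is diluted by 6/8, and the variance of the mean is (1 + 7 × 0.5)/8 = 0.5625. λ = 4 × 0.75²/0.5625 = 4 on 2 df: **42%**.
- Raw change from the single block-room baseline: variance 0.5 × (1/6 + 1) = 0.583. λ = 6.86 on 2 df: **65%**.
- Post-infusion mean with the block-room baseline as covariate: the variance of the mean is (1 + 5 × 0.5)/6 = 0.583, less 0.5² = 0.25, leaving 0.333. λ = 12 on 2 df: **88%**.
- The same with both pre-infusion values as covariates: 0.583 − 0.25 × 2/1.5 = 0.25. λ = 16 on 2 df: **96%**.

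**4. Other correlations (eight periods, two pre-infusion).**

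| Correlation | Interaction, 14 df | Raw change from baseline, 2 df | Baseline as covariate, 2 df |
|---|---|---|---|
| Exchangeable 0.3 | λ 8.57, 40% | 50% | λ 12.24, 89% |
| Exchangeable 0.5 | λ 12.00, 57% | 65% | λ 12.00, 88% |
| Exchangeable 0.7 | λ 20.00, 84% | 87% | λ 15.38, 95% |
| AR(1) 0.7 | λ 7.50, 35% | 39% | λ 7.91, 71% |

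The exchangeable rows use the formulas in step 3. The AR(1) row uses the same quantities with covariance 0.7^|i−j|.

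**5. Number of periods (ρ = 0.5).** With six periods, the interaction has λ = 4 × (2 × 4/6)/0.5 = 10.67 on 10 df, 58%. The covariate-adjusted comparison has variance (1 + 3 × 0.5)/4 − 0.25 = 0.375, so λ = 10.67 on 2 df, 84%. With nine periods the figures are 56% and 90%.

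**6. Why not a raw change score.** With three pre-infusion periods out of eight, the interaction has λ = 4 × (3 × 5/8)/0.5 = 15, 69%. Raw change from one baseline has variance 0.5 × (1/5 + 1) = 0.6, so λ = 6.67, 63%, below the interaction.

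**7. Why not only a 1-df dose score.** If 2 mcg/mL gave 5 mmHg and 5 mcg/mL gave 2.5 mmHg (SD 10, ρ = 0.5), a linear dose contrast on change would have 41% power. The 14-df interaction would have 81% and a 2-df comparison 98%.

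**The case against.** The strongest reply is that the plan does not rest on the interaction alone. It lists the group main effect and sizes it separately. A reader might infer that, if only post-infusion data were modelled, a constant effect would be found just 5% of the time, because it creates no interaction. That ignores the main effect, which in that model is the average arm difference after infusion start. It would have 65% power at ρ = 0.5, 80% at 0.3 and 66% under AR(1) 0.7. What remains is that the plan does not say which periods enter the model, and that these figures are still below the 88%, 89% and 71% obtained with baseline as covariate.

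Second, the degrees of freedom are an interpretation. The plan never calls the test omnibus. A scored dose would halve the df and raise power to 71% in the base case; linear time × group would give 65%. In the other direction, 14 is no ceiling: the protocol also says "patients will be randomly allocated by computergenerated randomization to one of four groups", and four arms with eight periods would give 21 df.

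Third, a steady effect is assumed. The protocol fixes the infusion rate, not the response, and patient-initiated boluses, vasoactive drugs, extra ropivacaine boluses and reduction of the epidural all vary over time. This stands, and it is the reason to keep the interaction as a secondary analysis.

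**Conclusion.** The point holds as a loss of efficiency and a missing specification. Under a sustained shift, the covariate-adjusted 2-df comparison beats the interaction in every scenario tabulated. The gain is 31 points at ρ = 0.5, 49 at 0.3, 36 under AR(1) 0.7 and 11 at 0.7. It shrinks as the effect or the correlation grows. These sizes rest on the assumed 0.4 SD steady effect with a half-size effect at the middle dose, eight periods, two of them pre-infusion, and 50 per arm.

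Three stronger readings are tempting and not supported:

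- **That the trial is underpowered against its own target.** The stated f = 0.09 for change is reproduced by an interaction test on 15 df under plausible inputs.
- **That a real effect would probably be missed.** The base case gives the interaction 57%. At the size in the plan's example, "assuming MAP has an SD = 10, the present study will be able to detect mean differences of 5 mmHg across groups", the 14-df interaction has 81% (ρ = 0.5, two pre-infusion periods).
- **That the answer on hypotension is compromised.** Aim 1a is addressed by logistic regression, which this point does not touch.

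**What to change.** In the Data analysis plan, make the main test for each continuous haemodynamic outcome the 2-df comparison of the three arms on the mean over the post-infusion periods, with the pre-infusion block-room value as a covariate. List the periods that count as post-infusion, and state how time and dose are coded. Do not use a raw change from the single baseline, which gives up most of the gain. Do not rely only on a 1-df dose score, because aim 2 asks which concentration is optimal and the response may not rise with dose. Adding the second pre-infusion value as a covariate is a further option (96% against 88% in the base case). Keep the time × group interaction as a secondary description of when the effect occurs.

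The cost is a sentence or two in the plan. The data are already scheduled, and the comparison can be estimated within the mixed model. The downside is that an effect that changes sign over time would be averaged out; the secondary interaction would still show it.

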Primary measurements:

Include the average invasively or non-invasively measured SBP, diastolic blood pressure (DBP), MAP, arterial blood oxygen saturation (SaO2), heart rate, respiratory rate, and pain by the visual analog pain score (VAS) on the "Defense and Veterans Pain Rating Scale" (DVPRS) measured over the following set periods:

Preoperative period

Primary measurements every 3 to 5 minutes and at indicated time points:

- I. Before the bolus epidural is injected.
- II. After the epidural bolus is injected but before anesthesia is induced.

Intraoperative period

Primary measurements every 3 to 5 minutes

Postoperative period

I. Primary measurements in the recovery room (if appropriate) every 15 minutes

II. Primary measurements following transfer to the floor every 4-6 hours if within normal limits, but every hour if needed for closer observation in case of possible abnormality for as long as the epidural analgesic blocks are continued, but at least every 8 hours after discharge from the PACU.

Secondary measurements:

[figure not shown]
- III. Spread of block per spinal root segment as tested by sensitivity to cold recorded every hour postoperatively and every 8 hours for the subsequent 72 hours after discharge from the PACU.
- IV. Ambulation on the first day after surgery (POD 1), POD 2 and 3, will be recorded per physical therapy protocol and distance ambulated per 24hour period will also be recorded. Physical Therapy information will be gathered to test motor effect on lumbar epidurals.
- V. Opioid usage data will be recorded and converted to morphine equivalents and averaged for POD 0, 1, 2, and 3 per group.
- VI. Side effects such as pruritus, nausea/vomiting, and respiratory depression (defined as respiratory rate less than 10 breaths per minute of oxygen saturation more than 7 points lower that the patients preoperative value on room air) will be recorded and managed as deemed appropriate by the attending physician.
- VII. 24 hour I/O for the first 72 hours to assess fluid balance, length of stay, and amount of days before return to PO status.

Data analysis plan

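### Logistic regression is the only method named for categorical outcomes, with no rule for sparse counts; for any uncommon side effect (about 5% or less) its estimates and P values would be unreliable

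*Combined protocol and SAP*

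**What the plan says.** Section 6, Data analysis plan, names logistic regression as the method for relating dose to "incidence of hypotension (SBP < 20% or MAP < 55 mmHg) and other categorical outcome variables". Among the categorical outcomes, Secondary measurements, item VI, lists "Side effects such as pruritus, nausea/vomiting, and respiratory depression", and Aim 1e asks whether epinephrine reduces them.

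The same section describes dose as "group (i.e., epinephrine dose; coded as an ordinal variable", but in the mixed-model sentence; the coding is not repeated for the logistic models. The threshold is general: "A P value of <0.05 was considered statistically significant for all statistical tests". No exact, penalised or other sparse-data method is named, and the type of test (Wald or likelihood-ratio) is not given.

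On numbers, Sample size determination says "At 80% power (alpha = 0.05), a sample of n=200 (50 per group". Only three arms are listed under Research-Related Procedures - Preoperative Period, starting with "Group A (Ropivacaine 0.2% infusion; Control group". If 200 patients are split over those three, each arm has 200/3, or about 67. (The conflict between three and four groups is a separate matter.) No expected rate is given for any side effect. For hypotension, section 4 speaks of "the high incidence of associated hypotension".

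**The concern.** The study infusions contain no opioid, so opioid-type side effects would come mainly from sedation and rescue drugs. Some, respiratory depression for example, could be infrequent. With 50 to 67 patients per arm, an infrequent event can easily be absent from one arm. Maximum-likelihood logistic regression then may have no finite estimate, and its two usual tests can give opposite answers on the same data.

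This bears on Aim 1e directly: if epinephrine does reduce a side effect, the epinephrine arms are the ones likely to be empty. As an illustration, assume true rates of 2% and 1% in the two epinephrine arms of 50. The chances of an empty arm are 0.98^50 = 0.364 and 0.99^50 = 0.605. At least one is empty with probability 1 − 0.636 × 0.395 = 75%, and both with probability 0.364 × 0.605 = 22%. The choice of test would then be made after the data are seen.

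**Working it through.** **The plan's own figure.** The plan says 50 per group detects a 26-point difference in categorical outcomes. With pooled variance, two-sided 0.05 and assumed rates of 45% v 19%: z = (0.26 × √50 − 1.96 × √(2 × 0.32 × 0.68)) / √(0.45 × 0.55 + 0.19 × 0.81) = (1.838 − 1.293) / 0.634 = 0.86, power 80.5%. The figure reproduces for a comparator near 45%, which the plan does not state. At 50% v 24% power is 77.7%; at 40% v 14% it is 84.4%. So the stated figure corresponds to a common outcome and says nothing about rare ones.

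**Two arms of 50, none v k events.** The maximum-likelihood odds ratio is infinite in each case. For k = 5, the likelihood-ratio (LR) statistic is 2 × [5 ln 0.10 + 45 ln 0.90 − 5 ln 0.05 − 95 ln 0.95] = 7.19, P = 0.007. Fisher's P is 2 × C(50,5)/C(100,5) = 0.056. Firth's odds ratio is (5.5/45.5)/(0.5/50.5) = 12.2.

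| k | Wald P | LR P | Firth P | Fisher P |
|---|---|---|---|---|
| 3 | 0.999 | 0.039 | 0.105 | 0.242 |
| 5 | 0.999 | 0.007 | 0.023 | 0.056 |
| 8 | 0.999 | 0.0006 | 0.002 | 0.006 |

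**Three arms of 50, events 4, 2, 0: coding matters.** With arm-level coding, the contrast with the empty arm is not finite: Wald (2 df) 0.71, LR 0.058, Firth 0.146. With a 0/1/2 dose score, the odds ratio is finite, 0.28 per step: Wald 0.069, LR 0.032, Firth 0.045.

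**How often no finite estimate exists.** Let p be an assumed common rate and q = (1 − p)^n.
- Arm-level coding: at least one arm empty but not all three, 1 − (1 − q)³ − q³.
- Dose score: all events in A only or C only, 2q²(1 − q).

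For example, at p = 5% and n = 50, q = 0.077, giving 21% and 1.1%.

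**Null rejection rates**, from enumerating the binomial outcomes with 50 per arm, nominal 5%:

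| Assumed rate | No finite estimate: arm-level / score | LR: arm-level / score | Wald, score | Firth: arm-level / score |
|---|---|---|---|---|
| 1% | 72% / 29% | 1.7% / 7.1% | 0.01% | 0.01% / 1.1% |
| 2% | 69% / 17% | 5.0% / 9.6% | 0.2% | 0.2% / 2.9% |
| 3% | 51% / 7% | 7.5% / 8.9% | 0.7% | 0.6% / 4.0% |
| 5% | 21% / 1.1% | 9.2% / 6.8% | 2.2% | 2.2% / 4.7% |
| 10% | 1.5% / <0.01% | 6.2% / 5.4% | 4.1% | 4.1% / 4.9% |

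The score here is 0/1/2. Scoring dose as 0/2/5 gives LR 8.8%, 7.7% and 6.2% at rates of 2%, 3% and 5%, and Firth 2.9%, 3.9% and 4.5%.

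With 67 per arm the pattern is the same but milder. At rates of 1%, 2%, 3% and 5%, no finite estimate exists in 75%, 57%, 34% and 9% of trials with arm-level coding, and in 25%, 10%, 3% and 0.2% with a score.

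**The case against.** A reader might infer more than the documents support, in four ways.

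- **Any empty arm gives an infinite odds ratio.** This is true only with arm-level coding. The one coding the plan mentions is ordinal. If that means a score, events of 0, 1, 3 give a finite odds ratio of 4.7 per step.
- **Whatever test is used, the P value is badly wrong.** The plan does not prescribe Wald tests. The LR test is moderately liberal, and below nominal with arm-level coding at a 1% rate. Fisher's test is itself conservative, so the gap between LR and Fisher overstates the LR error. For 0 v 5, Firth (0.023) falls on the same side of 0.05 as LR (0.007).
- **The side effects are rare.** No document says so. Patients may receive alfentanil, oxycodone and hydromorphone PCA, and nausea/vomiting may well be common.
- **Hypotension is affected.** It is described as frequent, and an empty arm is then very unlikely.

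Quoting the plain chance of any empty arm (94% at a 1% rate, 50 per arm) would also exaggerate. It includes the 22% of trials with no events at all, where there is nothing to estimate.

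All of this stands, and it is fair to add that an infinite odds ratio is visible in the output and that only secondary outcomes are involved. What remains is that the coding, the test and the fallback are all open, and that for an uncommon outcome these choices decide the answer.

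**Conclusion.** The point holds as a minor gap in the analysis of secondary side effects. It depends on one assumption that the documents can neither confirm nor exclude: that at least one side effect occurs in about 5% of patients or fewer.

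Under that assumption, when no finite estimate exists, the Wald P is near 1 and the Wald interval is useless. The LR test's type I error peaks at about 9% to 10%. At rates of 2% to 5% with 50 per arm, Firth's method stayed at or below 4.7% under every coding examined. At about 10% incidence or more, the problem all but disappears. Neither the hypotension analysis nor the sample size is called into question. The rates in the table assume equal incidence in all arms and a two-sided 0.05 level, which the plan does not state.

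**What to change.** In the Data analysis plan:

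1. State how dose enters the logistic models (arm-level indicators or a score, and which score).
2. State that side-effect outcomes with few or no events in any arm are analysed by Firth penalised logistic regression, with penalised-likelihood-ratio P values and profile-likelihood intervals. Define few by a count fixed before unblinding, for example fewer than five. A generous trigger does little harm: at 10% incidence Firth's rejection rate is 4.1% to 4.9%.
3. State that Firth is the governing analysis and that any exact test is descriptive only. Otherwise a result such as 0.023 by Firth and 0.056 by Fisher has no agreed reading.

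The cost is a sentence or two, with no added patients or data. A procedure other than the one intended in the named software may be needed. Firth is also conservative at very low rates: mildly with a dose score (2.9% at a 2% rate), markedly with arm-level coding (0.2%). That is a further reason to settle the coding in advance.
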